### 2.3 Preliminary Data

[figure not shown]

**Figure 1.** Microbial community diversity and intestinal permeability at study time points day 1, 8, and 15 for a cohort of 43 preterm infants (<33 weeks gestational age). Microbial community diversity is calculated as OTU richness based on 16S rRNA gene amplicon high-throughput sequencing. Intestinal permeability was calculated as the ratio of non-metabolized sugar probes

gestational age (<31.7wk) were identified to be the most discriminatory features for elevated IP by supervised learning scheme, reaching an accuracy of 86.1%. (5) *Clostridiales* and *Bifidobacteriales* are the most abundant bacteria groups in later stages (phase II/III at 6-18

Our analysis of the initial cohort of 43 preterm infants recruited for the IND protocol, and others' previous studies have shown that IP is high at birth in preterms (<33wk gestation) with a rapid maturation of the intestinal barrier over the first 2 weeks. However, in some infants, high IP persisted and/or recurred in association with altered levels of the normal microbiota (bacteria community composition). Specifically, we observed that (1) rapid maturation of intestinal barrier function, characterized by decreased IP, correlates with increased microbial community diversity (Figure 1), and most outstandingly, the increased abundance of beneficial bacteria *Clostridiales* (Figure 2); (2) *Clostridiales* is highly transcriptionally active and co-active with the probiotic bacterium *Bifidobacterium*; (3) neonatal factors, including early introduction of breast milk, shorter period of antibiotic exposure, and later gestational age, favor the early colonization of the gut microbiota by members of *Clostridiales* and *Bifidobacterium*, which altogether are associated with improved intestinal barrier in preterm infants; (4) low *Clostridiales* spp. abundance (<5%) and early

months of age) as shown in Figure 2, suggesting a process of gaining prosperity of these two bacterial groups during intestine development after birth. Altogether our preliminary results suggest the early colonization of the natural occurring probiotics strains *Clostridiales* and *Bifidobacterium* strongly associate with rapid maturation of intestinal barrier function, and their measurement are highly promising for early detection and as potential nutritional supplement to prevent NEC in the high-risk preterm population.

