**Secondary Objectives:**

- 1) To assess stool microbiome characteristics in association with intestinal permeability in preterm infants measured by the urinary lactulose/rhamnose ratio

- 2) *To analyze the correlation of stool calprotectin, sIgA, and lactoferrin to urinary lactulose/rhamnose ratio and stool microbiome characteristics in neonates born between 24 and 32 weeks of gestational age.*

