## 10 STATISTICAL CONSIDERATIONS

### 10.5 Sample Size Considerations

Sample size for primary objective: The sample size for the first aim (50 subjects) will provide good precision in the estimate of the distribution of levels of intestinal permeability at each time point. The quantiles will be accurate +/- 10 percentage points (based on a 95% confidence interval). Based on the sites' combined annual admission numbers and survival rates, we expect 120 infants to be eligible in the 6 month planned enrollment period in the first year. The combined NICU population is approximately 59% male with an ethnic distribution of 65% African-American, 33% Caucasian and 2% other.

Sample size for microbiome analysis: The sample size of 200 was calculated to obtain high precision in correlations between features of the stool microbiota and intestinal permeability (IP). Since 83% subjects in the first cohort had high IP ( $La/Rh \geq 0.05$ ) at study day 8, a sample size of 166-236 provides marginal error of 0.05 (maximum sampling error of 5%) and alpha of 0.05 (95% confidence level) to detect correlations between features of the microbiota and changes in IP and to achieve an expected sensitivity of 0.8-0.9 and expected specificity at 0.9-0.95.

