gestational age (GA) at 24-32 weeks, information including extensive data on demographics, obstetric and neonatal factors, medication exposures, and feeding practices will be obtained. Fecal specimen will be collected to generate bacterial community composition and structure using high-throughput sequencing of 16S rRNA gene amplicon and to calculate bacterial total copy number using quantitative PCR. Urine specimen will be used to measure the non-metabolized sugar lactulose (La) and rhmnose (Rh) concentration using high-pressure liquid chromatography (HPLC), and their ratio will be used to calculate high IP ( $La/Rh > 0.05$ ) and low IP ( $La/Rh \leq 0.05$ ). (2) Discriminatory classifier generation. The bacterial abundance and neonatal information will be used to form the data matrix and the high or low IP category will be used to “label” a sample as its class, which is used in supervised machine learning scheme with cross-validation (construct model on a sample set and evaluate on a different sample set to avoid over-prediction) to direct generating the classifier after data preprocessing and evaluation. The most discriminatory features (i.e. bacterial species and/or neonatal factors) will be characterized by its contribution to identify a sample in a high or low IP class. (3) We will evaluate the contribution of each discriminatory feature to IP classification using permutation importance measurement (5).

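### The microbiome objective concerns association with the La/Rh ratio, but the only method written for it is a classifier on the ratio cut at 0.05; a pre-specified continuous analysis should be added

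*Combined protocol and SAP*

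**What the plan says.** Secondary objective 1 (Section 2.5) is "To assess stool microbiome characteristics in association with intestinal permeability in preterm infants", with permeability measured by the urinary La/Rh ratio. Section 3.2 lists permeability as a quantitative outcome and leaky gut as a binary one. The sample-size text (Section 10.5, Sample Size Considerations) says that 200 was chosen for "high precision in correlations between features of the stool microbiota and intestinal permeability".

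Section 10.6 treats the outcome differently for different markers:

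- **Calprotectin, sIgA and lactoferrin:** Pearson correlation with the La/Rh ratio, or Spearman if a variable is clearly skewed, plus ROC analysis at a cut of 0.05.
- **Gestational age, birthweight, sex and feeding type:** terms in a mixed model for La/Rh.
- **Microbiome:** laboratory methods and abundance calculation, then a cross-validated classifier. Each sample's class is its permeability category at 0.05 ("and the high or low IP category will be used to" label it), and features are ranked by permutation importance.

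No correlation or regression of a microbiota feature on the continuous ratio is described.

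**The concern.** The feature that drove the enlargement to 200 infants has no continuous analysis, while the three stool proteins have one. A classifier and its importance ranking show which features help to sort infants into two groups. They do not say how strongly Clostridiales abundance, for example, goes with La/Rh, or how precisely that is known. So objective 1, and the precision in correlations claimed for N=200, have no planned result that answers them.

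Cutting the ratio can also cost sensitivity. It treats an infant just above 0.05 as the opposite of one just below it, and as equal to one far above it. The split is expected to be uneven, which makes the loss larger under the usual model. Real associations could be missed. If a correlation analysis is added after the data are seen, the choice of taxa, scale, stool sample and covariates will be open to question.

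**Working it through.** **Inputs from the documents**

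- Share with high permeability: 0.83 ("Since 83% subjects in the first cohort had high IP", Section 10.5), at study day 8 with cut-off >=0.05.
- Size of that cohort: at most 43 ("Our analysis of the initial cohort of 43 preterm infants recruited for the IND protocol", Section 2.3, Preliminary Data).
- Planned N: 200. Margin 0.05, two-sided alpha 0.05, "expected sensitivity of 0.8-0.9 and expected specificity at 0.9-0.95" (Section 10.5).

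**Assumptions, not in the documents:** the analysed outcome (for example log La/Rh) is roughly normal, the association is linear, and r=0.2 is an illustrative correlation.

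**1. The plan's own range of 166-236.** The formula for estimating a sensitivity to a given margin is n = 1.96² × Se(1−Se) / (0.05² × 0.83).

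- Se 0.90: 3.8416 × 0.09 / 0.002075 = 166.6, which matches 166.
- Se 0.85: 3.8416 × 0.1275 / 0.002075 = 236.0, which matches 236.
- Se 0.80, the stated lower value: 296.2, which does not match.

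The range thus reproduces for sensitivities of 0.85 to 0.90. That mismatch is a separate matter. What counts here is that no correlation enters a formula that gives both ends of the range, although the text justifies 200 by precision in correlations.

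**2. Size of the classes.** 200 × 0.17 = 34 infants with low permeability, against 166 with high.

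**3. Information kept by the binary label.** For a normal outcome cut at quantile p, with z_p the normal quantile and φ the normal density, the share kept is φ(z_p)² / [p(1−p)]. At p = 0.83, z_p = 0.954 and φ² = 0.0641, so the share is 0.0641 / 0.1411 = 0.454. The loss is 54.6%, and 200 infants act like 200 × 0.454 = 91. A true correlation shrinks by √0.454 = 0.674.

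**4. Power for one feature at r = 0.2, N = 200.** Using Fisher's z, power = Φ(atanh(r)√197 − 1.96).

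- Continuous: atanh(0.2) × 14.04 − 1.96 = 0.886, power 81%.
- Binary: effective r = 0.674 × 0.2 = 0.135, giving −0.057, power 48%.
- Smallest r detectable with 80% power: 0.197 continuous, 0.197 / 0.674 = 0.29 binary.

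Simulation with normal data gave 81% and 49%.

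**5. Uncertainty in the 83%.** If it stands for 35 or 36 of 43 infants, the exact 95% intervals together run from 67% to 93%. Repeating steps 3 and 4:

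| High-permeability share | Information lost | Power at r = 0.2, binary |
|---|---|---|
| 70% | 42% | 57% |
| 83% | 55% | 48% |
| 92% | 70% | 34% |

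The continuous analysis has 81% power in every row.

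**6. If the outcome is not normal.** Simulations at the 83/17 split, with r of 0.2 and 0.3, compared the squared correlation of the binary label with that of the continuous outcome. The normal value is about 0.45.

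- Heavy-tailed errors: 0.69 to 0.84 against Pearson, 0.40 to 0.42 against Spearman.
- Errors with a long lower tail: 0.21 to 0.22 against Pearson, 0.11 to 0.13 against Spearman.
- Errors with a long upper tail and a sharp lower edge: above 1 against either, so the binary label did better.

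The size, and in an extreme case the direction, depends on the distribution.

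**The case against.** The best defence is that the binary label serves an aim the protocol states. The Endpoints entry of the Protocol Summary ties microbiome changes to impaired barrier function at La/Rh >=0.05. Section 2.3 (Preliminary Data) looks for rapid detection of abnormal permeability, and the sample-size text quotes sensitivity and specificity. A classifier at a fixed cut-off suits that question. This stands, and the classifier should be kept.

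It is also fair to say that the power figures describe a single-feature linear test, whereas the plan has a multi-feature classifier with no per-feature test. The preliminary discriminating features were themselves thresholds (Clostridiales below 5%, gestational age below 31.7 weeks), so linearity is not assured. The 83% comes from a small cohort at study day 8 with cut-off >=0.05, while the classifier uses >0.05 at 7-10 days. These points limit how firmly any single figure can be stated. They do not supply the missing association analysis.

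A reader might infer that the sponsor decided to discard the continuous ratio. The documents do not support that: the objective, the quantitative outcome and the sample-size text all point to an intended analysis of the ratio. What is missing is a method for it.

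**Conclusion.** The concern holds as a gap between objective and method: association with the ratio is intended, and the only microbiome method written down dichotomises it and gives no estimate or interval for the association.

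The loss of about 55% is conditional on normality on the analysed scale, a linear association and the 83% share; over shares of 70% to 92% it is about 42% to 70%. It would be tempting to say that the study will in fact lose more than half of its information, or that 200 infants are in effect 91. The documents do not support that as a fact, because they give no La/Rh distribution, and the simulations with skewed errors show that the figure can move a long way in either direction.

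The objective is secondary, the study is not randomised, and the primary objective (the distribution of La/Rh) is unaffected. This is a cheap improvement.

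**What to change.** Add to Section 10.6 a pre-specified analysis for secondary objective 1:

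- **Outcome:** continuous La/Rh, on the log scale, or by Spearman or another rank method if it remains skewed. This follows the rule already given for the stool proteins.
- **Features:** Clostridiales abundance, Bifidobacterium abundance and community diversity, each reported with an estimate and 95% interval.
- **Stool sample:** one defined sample per infant, because each infant has a single La/Rh test but serial stools to day 14 and on day 21. An example is the sample nearest to, and not after, the test.
- **Adjustment:** gestational age and postnatal age at test.
- **Other taxa:** false-discovery-rate control.

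Keep the high/low classifier as a separate analysis for the detection aim.

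The change needs no additional infants, visits or samples. It costs some specification now, chiefly the choice of stool, and a second set of microbiome results to report beside the classifier.

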#### **6.8 Final Study Visit (include allowable time window)**

##### **PND21 (± 2d) or discharge/transfer whichever comes first**

- ∞ *Final collection of stool samples for analysis*
- ∞ Medication history including the number of packed red blood cell transfusions and total volume received will be collected from the chart
- ∞ *Record daily weight, and weekly height, and head circumference.*
- ∞ Collection of adverse events from medical chart.

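### The classifier plan does not keep label-based selection inside the training folds, split folds by infant, or stop predictors at the La/Rh test, so it does not protect the reported performance from inflation

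*Combined protocol and SAP*

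**What the plan says.** The validation plan for the classifier is a few lines of section 10.6, under Discriminatory classifier computation. Bacterial abundance and neonatal information form the data matrix, and each sample is labelled as high or low permeability from the urine La/Rh ratio. The model is built "with cross-validation (construct model on a sample set and evaluate on a different sample set to avoid over-prediction"; the same sentence then says that this scheme serves "to direct generating the classifier after data preprocessing and evaluation". Next, "The most discriminatory features (i.e. bacterial species and/or neonatal factors) will be characterized by its contribution" to the classification, and a third step ranks features by permutation importance.

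The section names no algorithm, number of folds, outer loop, held-out set or performance measure for the classifier. It does not define the preprocessing. It does not say whether the labelled sample is a stool or an infant.

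On timing, the La/Rh test that fixes the label is given once between day 7 and day 10 (section 6.9). Stool collection continues to day 14 with one more sample on day 21 (section 6.4). At the final visit, on day 21 ± 2 or at discharge or transfer if earlier, "Medication history including the number of packed red blood cell transfusions and total volume received will be collected from the chart" (section 6.8). Section 10.6 ties the clinical data to recruitment before 5 days of age but gives no end date for medication or feeding exposure.

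**The concern.** Cross-validation gives an honest estimate only if every step that uses the labels is repeated without the held-out samples. Here the same cross-validation also steers how the classifier is made, and the text does not say which steps sit inside it. An analyst could follow section 10.6 to the letter and still select features or tune settings on all labels. Stools from one infant could also fall on both sides of a split, and exposures or stools that post-date the test could enter as predictors.

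Section 2.3 states the aim of an accurate and rapid way to detect abnormal permeability. If labels leak, uninformative features can look like a useful test. If predictors post-date the test, the model cannot support detection at the time of testing, even if the association is genuine.

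**Working it through.** **Inputs from the documents.** N = 200, and "Since 83% subjects in the first cohort had high IP" (section 10.5, Sample Size Considerations). This gives 200 × 0.83 = 166 high and 200 × 0.17 = 34 low.

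**The plan's own figure.** The plan gives no figure for validation. The nearest is the sample-size range 166-236, stated for "expected sensitivity of 0.8-0.9 and expected specificity at 0.9-0.95" with a margin of 0.05. With N = 1.96² × p(1 − p) / 0.05² / 0.83:

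- p = 0.90: 138.3 / 0.83 = 166.6
- p = 0.85: 195.9 / 0.83 = 236.0
- p = 0.80: 245.9 / 0.83 = 296.2

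The range therefore matches sensitivity 0.85-0.90, not 0.80-0.90. That is a separate matter. What counts here is that only about 34 infants carry the low label.

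**Assumptions, because the documents give none.** Independent standard normal noise features, 10 features picked by t statistic, ridge-regularised linear discriminant analysis, stratified 10-fold cross-validation, 150 runs per setting. The true AUC is 0.50 throughout.

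**1. Where selection is done (mean AUC).**

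| Candidate features | Selected on labels before the folds | Selected inside each fold | Label-blind scaling first, selection inside folds |
|---|---|---|---|
| 50 | 0.698 | 0.499 | 0.510 |
| 100 | 0.746 | 0.496 | 0.491 |
| 300 | 0.809 | 0.504 | 0.499 |
| 1000 | 0.856 | 0.510 | 0.497 |

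A repeat of the first three settings with selection before the folds gave 0.70, 0.75 and 0.80. Preprocessing that does not use the labels caused no inflation.

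**2. Tuning without an outer loop.** Selection was inside the folds, but the best of 8 settings for the number of features was reported (60 runs). Mean AUC was 0.571 with 100 features and 0.576 with 300, with 95th percentiles of 0.690 and 0.698. A repeat gave means of about 0.53-0.56 and 95th percentiles of 0.66-0.68.

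**3. Fold unit.** Assumed 3 or 8 stools per infant, within-infant correlation 0.3 to 0.7, 20 noise features, 5-nearest-neighbour classifier, 8 runs per setting.

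| Stools per infant | Correlation | Folds split by sample | Folds split by infant |
|---|---|---|---|
| 3 | 0.3 | 0.581 | 0.524 |
| 8 | 0.3 | 0.581 | 0.493 |
| 3 | 0.5 | 0.712 | 0.499 |
| 8 | 0.5 | 0.827 | 0.483 |
| 3 | 0.7 | 0.905 | 0.516 |
| 8 | 0.7 | 0.991 | 0.491 |

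**4. Predictor timing.** The label dates from day 7-10. Stools run to day 14 and day 21, and medication and transfusion history runs to day 21 ± 2. No section restricts the data matrix to what was known at the test. The documents do not allow the effect to be estimated. As a scale only, a single normal predictor that differs between classes by d standard deviations has AUC = Φ(d/√2). That is 0.57 for d = 0.25, 0.64 for d = 0.5 and 0.76 for d = 1.0.

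**5. Why intervals and class-specific measures are needed.** The 95% half-width is 1.96 × √(p(1 − p)/n). For sensitivity 0.90 with n = 166 it is 0.046. For specificity 0.95 and 0.90 with n = 34 it is 0.073 and 0.101. Calling every infant high gives 166/200 = 83% accuracy, close to the 86.1% reported for the pilot classifier in section 2.3, so accuracy alone says little.

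**The case against.** The plan does contain protective wording. It says that the model is evaluated on samples different from those used to construct it, and that the purpose is to avoid over-prediction. It describes no label-based filter before the folds. In its order of steps, features are characterised after the classifier has been generated. The preprocessing may be no more than data cleaning or label-blind normalisation, which the check shows to be harmless. The only timing attached to the clinical data is recruitment before 5 days of age, and the final-visit list does not say that day-21 totals enter the classifier. The classifier is also not named among the primary or secondary objectives in section 2.5.

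All of this stands against a stronger reading. A reader might infer that the model is graded on the very data that shaped it, that preprocessing on all samples inflates the result, or that exposures after the test are meant to be used. The documents state none of these.

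It does not close the gap. Evaluating on different samples is an aim that selection or tuning on all labels can still defeat. The recruitment wording cannot be a cut-off for everything in that data-collection step, because the step also covers the urine test, which comes days later. Permutation importance ranks features; it does not correct a biased performance estimate.

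**Conclusion.** The concern holds as an omission. One cross-validation both directs the making of the classifier and supplies its only evaluation. The plan leaves open where label-based steps are done, what the fold unit is, and when predictors stop.

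The size depends on what is actually done. If features are selected on the labels before the folds, noise alone gives a mean AUC of about 0.70-0.81 with 50 to 300 candidates. Reporting the best of 8 un-nested settings gives about 0.53-0.58. Selection inside the folds gives about 0.50. Splitting repeated stools by sample can inflate as much or more (0.58-0.99), depending on the correlation between stools of one infant. These figures rest on assumed feature counts, fold numbers, correlations and simple classifiers. They show what the text leaves possible and do not forecast the trial's result. The timing gap is a matter of validity for detection, and its size cannot be derived from the documents.

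**What to change.** Amend section 10.6, Discriminatory classifier computation, to state that:

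- performance is estimated by nested, repeated cross-validation, with all folds, inner and outer, split by infant;
- all filtering, feature selection, tuning and threshold choice that uses the La/Rh label is done inside the training folds;
- AUC, sensitivity and specificity are taken from the outer folds only and reported with intervals;
- only stools and time-varying exposures (antibiotics, transfusions, feeding) dated up to the La/Rh dose that supplies the label enter the data matrix.

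Later stools and exposures remain available for the descriptive microbiome analyses.

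The cost is a few sentences of analysis plan and more computing time. No new visit, sample or procedure is needed: stool collection starts by day 5 or within 24 hours of enrolment, and medication is already reviewed at the visits on days 0-5 and 7-10 (Appendix A). The downside is that the reported performance will probably be lower. If the team already intends to work this way, writing it down costs almost nothing.

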## **10.7 DATA HANDLING/RECORD KEEPING/Source Documents**

All record keeping procedures will maintain participant confidentiality in accordance with ICH-GCP guidelines. Paper records will be kept locked and only study staff will have access to study records. Accuracy will be ascertained through the study quality assurance plan. Details are listed in the Manual of Procedures.

